## 5. REGISTRY OBJECTIVE AND PURPOSE

---

### 5.1 Objective(s)

---

The purpose of this registry is to observe the effects of Varithena® on VLU healing in patients who have the symptoms of chronic venous insufficiency. The objective of the registry is to evaluate VLU healing rate, recurrence rate, and patient reported outcomes for Varithena® in C6 disease per Clinical Etiologic Anatomic Pathophysiologic (CEAP) classification

### 5.2 Design

---

[figure not shown]
This 12 month, multicenter, open-label registry is designed to collect treatment and outcome data related to subjects treated with Varithena® for GSV system and/or AASV incompetence resulting in VLU. Subjects are treated per Investigator's SoC and in accordance with the FPI and IFU. For subjects with healed ulcers during the 12 month follow-up period, VLU recurrence information is collected. Wound recurrence is defined as the reopening of a wound that was previously closed; recurrence must occur at same location.

Note: In cases of cluster wounds, Investigator collects data for a single, primary wound. If more than one wound meets eligibility criteria, Investigator determines which wound to evaluate as the primary. All endpoint measurements are collected for the primary wound.

For each subject, participation in the registry lasts approximately 12 months. Subjects are seen at the investigational site for initial treatment, about one week after treatment for initial follow-up visit (and retreatment if necessary), 12 weeks ( $\pm 1$ wk) and 12 months ( $\pm 1$ wk) after initial treatment. Between follow-up visits, and until wound closure, subjects are asked to collect weekly photographs of the wound via the sDCT during dressing changes at the wound care center (WCC).

Additionally, follow-up phone calls are placed at 3 months ( $\pm 1$ wk) post-closure and 6 months ( $\pm 1$  week) post-treatment. At that time, subjects are asked to take a picture of the wound area and complete the NPRS using the sDCT. (Figure 1)

Figure 1. Study Schematic

### 5.3 Primary Endpoint(s)

- Rate of epithelial migration (mm/week) measured by wound perimeter on photograph taken using the DCT and submitted to Tissue Analytics® for analysis
- Wound closure at 12 weeks ( $\pm 1$ wk) post-treatment
- Time from initial treatment with Varithena® to wound closure

## 5.4 Secondary Endpoint(s)

---

- Percent of wounds remaining closed at 3 months ( $\pm 1\text{wk}$ ) post-wound closure date, determined via photograph assessed by Tissue Analytics®; non-healed wounds are not included in percent calculation
- For healed wounds, rate of VLU recurrence collected via phone calls and subject-collected photographs at 6 months ( $\pm 1\text{wk}$ ) and 12 months ( $\pm 1\text{wk}$ ) post-treatment
- Change in pain on NPRS compared to baseline at 12 weeks ( $\pm 1\text{wk}$ ), 6 months ( $\pm 1\text{wk}$ ), 12 months ( $\pm 1\text{wk}$ ) post-treatment
- Change on EQ-5D-5L quality of life assessment compared to baseline at 12 weeks ( $\pm 1\text{wk}$ ) and 12 months ( $\pm 1\text{wk}$ ) post-treatment
- Change in VCSS from Baseline to 12 week ( $\pm 1\text{wk}$ ) and 12 month ( $\pm 1\text{wk}$ ) follow-up
- Number of ulcer free weeks defined as weeks from time of closure (complete epithelialization is recorded) to date of recurrence or last contact if no recurrence (at study completion or withdrawal)

## 6. SUBJECT SELECTION

---

### 6.1 Registry Population

---

This registry is designed to collect data related to treatment with Varithena® in patients experiencing symptoms of chronic venous insufficiency of the GSV or AASV system who are classified C6 on the CEAP with active VLU.

Data is collected for up to 200 subjects selected by their physician to receive Varithena®. Enrollment is to occur at up to 40 investigational sites in the United States and Canada.

### 6.2 Subject Selection

---

#### 6.2.1 Inclusion Criteria

---

Subjects must meet all of the following inclusion criteria:

- 1 Men and women; age  $\ge 18$
- 2 Investigator has selected Varithena® to treat patients classified C6 with chronic ( $\ge 3$  months) VLU resulting from GSV and/or AASV incompetence
- 3 Wound can be visualized in one plane to allow for image collection of the entire wound in one photograph, or if wound is circumferential, subject must be able to capture the entire wound using multiple photographs taken from directly above the wound (straight on)
- 4 Reflux  $>500\text{ms}$  on duplex ultrasound
- 5 Willing and able to collect wound photographs and data using an application downloaded on a tablet
- 6 Willing and able to return for scheduled follow-up and wound care visits
- 7 Ability to comprehend and sign ICF and complete questionnaires

## 6.2.2 Exclusion Criteria

---

Subjects must not meet any of the following exclusion criteria:

- 8 Contraindications to Varithena® in accordance with the FPI
- 9 Any serious concomitant disease, per physician's discretion, that confounds wound healing, including malignant changes of wound
- 10 Concomitant heat ablation, or heat ablation of index leg within 6 weeks prior to treatment with Varithena®
- 11 Significant arterial disease or ABPI ≤ 0.8
- 12 In the opinion of Investigator, wound would close within 12 weeks without additional treatment

## 6.3 Subject Completion

---

A subject is considered to have successfully finished the registry upon completion of the 12 month follow-up phone call.

## 6.4 Withdrawal

---

For cases in which the subject does not complete all assessments and follow-up visits, the subjects are classified as follows:

- Investigator withdrawal – Investigator can withdraw a subject from the registry for a safety concern, non-compliance, or for any other concern warranting withdrawal of the subject in the judgment of Investigator. Reason for Investigator withdrawal of a subject and last date of contact for the registry are documented on the Completion Log.
- Subject withdrawal – Subjects may withdraw from participation at any time during the registry. All data collected prior to withdrawal shall remain part of the registry data. Reasonable effort should be made to encourage the subject to remain in the registry. If the subject declines, determine and document the reason for withdrawal on the Completion Log.
- Lost to follow-up – A subject is considered lost to follow-up if there have been at least three documented attempts to contact the subject for follow-up without success. Last date of contact is documented on the Completion Log.

## 7. TREATMENT OF SUBJECTS

---

### 7.1 Varithena® (polidocanol injectable foam) 1%

---

Treatment with Varithena® is selected and administered per SoC and the FPI. Varithena® is commercially available. As such, investigational product (IP) accountability and tracking is not necessary.

#### 7.1.1 Dosage & Administration

---

Subject is treated on Day 0 with up to 15mL of Varithena®, above and below the knee as needed, per Investigator's clinical judgement and the FPI. Each injection should not exceed 5mL. Date of treatment, number of injection sites, and volume above and below the knee is recorded in the iDCT. Appendix E: Use of Varithena® to manage patients with GSV-derived venous hypertension and chronic venous leg ulcer is provided as a guide to best practices in treating this indication.

### 7.1.2 Additional Treatment

Additional treatment(s) of Varithena® can be administered at Investigator's discretion and according to FPI. Note that additional treatment should not be administered sooner than 5 days after previous treatment. Date of additional treatment, number of injection sites, and volume above and below the knee is recorded in the iDCT.

### 7.1.3 Post-treatment Management

Following treatment with Varithena®, subjects should be treated with compression dressing per Investigator's SoC. Subjects are referred to a local WCC. The WCC does not need to be affiliated with the investigational site. Subjects' compression dressing is checked and changed at the WCC. Subjects are asked to continue to visit the WCC weekly for continuing care until the wound is healed. At each WCC when the wound area is exposed, the patient should make every effort to take a photograph of the wound, or the wound area if the wound has healed, using the sDCT. The pain rating should also be recorded in the sDCT by response to the NPRS. The staff at the WCC are not delegated under the investigational site, so the subject should understand that they are responsible for collecting the photograph and answering the NPRS question independently.

If the wound is not healed at the 12 Week Follow-up visit, the subject continues to visit the WCC for continuing care until wound closure, collecting a wound photograph and answering the NPRS question at each appointment.

### 7.1.4 Duration of Treatment and Follow-up

Following the initial treatment with Varithena®, each subject is followed for 12 months. Additional treatment can be administered following the initial treatment; however, it is recommended that re-treatment occur as close to the time of the initial treatment as is possible, but not sooner than 5 days, according to FPI and IFU. Date of re-treatment, number of injection sites, and volume above and below the knee is recorded in the iDCT.

During the follow-up period, subjects are followed for VLU-related hospitalizations, wound recurrence, and other clinical outcomes. Subjects are assessed at the investigational site at Week 1 Follow-up visit (about one week after treatment), 12 weeks ( $\pm 1$  wk) post-treatment and 12 months ( $\pm 1$  wk) post-treatment. Subjects are contacted by telephone for follow-up 3 months ( $\pm 1$  wk) post wound-closure, and 6 months ( $\pm 1$  wk) post-treatment. Subjects collect wound photographs between follow-up visits when the wound dressing is being changed at the WCC.

### 7.1.5 Concomitant Therapies or Interventions

Subjects should not be enrolled in the registry if they were treated for venous insufficiency in the index leg with heat ablation above the knee within the 6 week period prior to enrollment.

Treatment with heat ablation could confound the outcome of treatment with Varithena®. For subjects who have had recent heat ablation treatment (greater than 6 weeks but less than 6 months), it should be clear to Investigator that ulcer is not healing or would not heal were subject not to receive additional treatment.

It is suggested that heat ablation not be used after treatment until the primary endpoint data have been collected at Week 12 Follow-up visit. This allows for assessment of the effects of Varithena® without heat ablation as a confounding factor.

## 8. MEASUREMENTS AND EVALUATIONS

---

### 8.1 Time and Event Schedule

---

#### 8.1.1 Screening/Baseline Visit (can occur up to 14 days prior to treatment) (Clinic)

---

The screening phase begins when the ICF is fully signed and dated and ends at the initiation of initial treatment with Varithena® (Day 0).

The following evaluations are performed at Screening/Baseline:

- Review and signing of the ICF
- Review and confirmation of eligibility to participate in the registry
- Collection of demographic information, wound history (including prior treatments), and physical examination to assess venous and wound characteristics
- Collection of photograph (photographs if wound is circumferential) in iDCT

#### 8.1.2 Enrollment/Treatment Visit (Day 0) (Clinic)

---

Screening/Baseline and Enrollment/Treatment visit measurements and evaluations may occur at the same visit if subject is provided adequate time to consider and have all questions answered.

The following are performed at this visit:

- Collection of data prior to treatment:
  - Photograph(s) of wound in iDCT
  - VCSS
  - NPRS
  - EQ-5D-5L quality of life assessment
- Varithena® Treatment – treatment procedure and collection of treatment details

#### 8.1.3 Week 1 Visit (1st Follow-up Visit Per SoC) (Clinic)

---

This visit is not required to occur within first week after initial treatment but should be the first follow-up visit per SoC. If retreatment is expected, this visit should occur no sooner than 5 days after initial treatment. Date of visit is documented in the iDCT.

The following are performed at the Week 1 visit:

- Subject is trained to use sDCT
  - Subject collects photograph(s) of wound using sDCT (additional training required for circumferential wounds)
  - Subject enters NPRS response into sDCT
- Assessment of medical compression therapy compliance
- Documentation of re-treatment details, if applicable

#### **8.1.4 Week 2 through Wound Closure (at WCC)**

---

The subject does not return to the investigational site at this time. The subject presents to a WCC for wound care and dressing changes on about a weekly basis. During each visit to the WCC, subject is asked to take a photograph (multiple photographs for circumferential wounds) of the wound and answer the NPRS question using the sDCT. It is important that the subject understands that the WCC staff may not be aware of the registry, so collection of the photograph(s) and answering the NPRS question should be completed independently. The subject should refer questions about the sDCT and data collection to the investigational site, or contact Tissue Analytics® for technical support.

If the wound is not healed at the Week 12 Follow-up visit, subject continues to collect photograph(s) and answer NPRS questions at weekly WCC visits until wound closure.

#### **8.1.5 Week 12 Visit (±1wk) (Clinic)**

---

The following are performed and entered into the iDCT at this visit:

- Collection of wound photograph(s) or photograph of wound area if wound is healed
- VCSS
- NPRS
- EQ-5D-5L quality of life assessment
- Assessment of medical compression therapy compliance

#### **8.1.6 3 Months (±1wk) Post-Wound-Closure (Telephone)**

---

Once the subject's wound is determined to be healed, Tissue Analytics® schedules a reminder for Investigator or delegate to contact the subject by phone at 3 months (±1 week) to perform the following:

- Assessment for VLU recurrence
- Assessment of medical compression therapy compliance
- Request that subject collects the following using the sDCT:
  - Photograph of wound area, or wound if reoccurred
  - NPRS

#### **8.1.7 6 Months (±1wk) Post-Treatment (Telephone)**

---

Investigator or delegate contacts the subject by phone to perform the following:

- Assessment for VLU recurrence
- Assessment of medical compression therapy compliance
- Request that subject collects the following using the sDCT:
  - Photograph of wound area, or wound if reoccurred
  - NPRS
- EQ-5D-5L quality of life assessment (only collected at 12 Months)

### 8.1.8 Month 12 Visit ( $\pm 1\text{wk}$ ) Post-Treatment (Clinic)

The following are performed and entered into the iDCT at this visit:

- Assessment for VLU recurrence
- Collection of photograph of wound area, or wound if recurred
- VCSS
- NPRS
- EQ-5D-5L quality of life assessment
- Assessment of medical compression therapy compliance

## 8.2 Evaluations and Procedures

Evaluations and procedures performed to establish eligibility and baseline may be performed within the 14 days prior to treatment, inclusive of day of treatment, provided subject has adequate time to consider and have all questions answered before treatment is initiated.

### 8.2.1 Informed Consent Process

Patients with the potential to meet eligibility criteria may be offered the opportunity to be evaluated for participation in this registry. All such patients must sign an ICF approved by the relevant Institutional Review Board (IRB) or Research Ethics Board (REB) before any trial-related evaluations can be performed.

Investigator or qualified delegate reviews the treatment plans with the patient and the patient has an opportunity to ask questions about trial procedures, the follow-up schedule, risks and benefits of the treatment and alternative treatment options prior to signature. The patient receives a copy of the signed ICF to keep for their records.

Subjects will be informed of any revisions of the ICF and relevant revisions are signed and kept in the subject's file.

The consenting process, acquisition of the ICF and any revisions should be documented in the subject's medical record and the ICF should be signed and dated by the individual who conducted the informed consent discussion.

### 8.2.2 Eligibility Review

A physical evaluation of the wound as well as data regarding venous insufficiency, medical history and prior treatment are reviewed against the eligibility criteria to determine eligibility of the subject for the registry. Subjects who complete a consent form and are found to be ineligible for the registry are recorded on the Screening Log with the exclusionary criteria indicated. Subjects who are found to meet all inclusion criteria and no exclusion criteria are entered into the iDCT.

### 8.2.3 Assignment of Subject Identification Code (SIC)

Subjects who meet all inclusion and no exclusion criteria for the registry are assigned an SIC by Investigator or delegate. The SIC is used to deidentify subject data and should be used on source worksheets and for data entry purposes. The Investigator or delegate maintains an SIC list, a confidential list of subjects' names and associated SICs which allows Investigator to determine identity of all subjects.

The SIC is formatted as a six digit number: a three digit assigned site code followed by consecutive three digit numbers, beginning with 001 (e.g., 321-001). The site code is provided to investigational site during site initiation.

#### 8.2.4 Demographics

---

For each subject, date of birth and gender are collected.

#### 8.2.5 Physical Examination

---

All patients undergo a physical examination at screening, in accordance with Investigator's current practice, to include height and weight.

The venous evaluation includes:

- Examination of the external appearance of the leg to be treated
- Confirmation of CEAP classification (Appendix A)
- Venous duplex ultrasound to review for duplex reflux duration, GSV, AASV, major perforator, and SSV incompetence

The wound examination includes:

- Location of index wound
- Number of current ulcers
- Signs of infection or bioburden

#### 8.2.6 Wound History and Prior Treatments

---

Information is collected regarding wound age at first encounter (defined as time since current episode began), total previous episodes of current ulcer and other ulcers, duration of compression therapy for current wound, and medical compression therapy compliance.

The following information is recorded for previous treatments (e.g., heat ablation, grafting) for the current ulcer. Treatment should only be listed for the current location of venous insufficiency and the resulting current ulcer:

- Procedure type
- Date (start date in the case of a long term treatment, like compression therapy)
- Outcome (i.e. Healed/Non Healed)

#### 8.2.7 Wound Photographs

---

Wound photographs for the registry are collected via the iDCT and sDCT. Photographs are analyzed for wound characteristics by Tissue Analytics®. Wound photographs are collected by Investigator or delegate at Baseline/Screening, Day 0 before treatment and Week 12 Follow-up visit using iDCT. Wound photographs are collected by subject via sDCT at Week 1 Follow-up visit, weekly during dressing changes at the WCC and at the 3, 6 and 12 month follow-up assessment time points. All photographs for a given subject are linked back to Investigator data using the SIC and are accessible by Investigator or delegate within the iDCT.

Investigator or delegate provides Tissue Analytics® sDCT training module to subject during Week 1 Follow-up visit and ensures subject can use sDCT. The photograph(s) collected at this visit should be collected by subject using the sDCT.

If the wound is circumferential, wound can be captured using two or more photographs. The subject should be able to view and photograph the entire wound using multiple photographs. The photographs should be taken from directly above and perpendicular to the wound (straight on). As this may be difficult for wounds that reach the back of the leg, it should be confirmed at screening that the subject is able.

### 8.2.8 Varithena® Treatment Record

---

The following data is recorded in the iDCT for the initial treatment with Varithena® and any touch up treatment:

- Treatment date
- Volume injected above the knee
- Volume injected below the knee
- Total number of injection sites (for specified treatment date)

### 8.2.9 Numeric Pain Rating Scale

---

An 11-point NPRS is used to assess subject's level of pain. Subject is asked "What was your pain level at the ulcer location over the last 24 hours?" and selects a score between 0 and 10, with 0 meaning no pain and 10 meaning the worst pain. Investigator or delegate assesses and records this directly into the iDCT. The subject answers this question in the sDCT at Week 1 Follow-up visit, at each weekly WCC visit during dressing changes and at 3 months post wound closure, and 6 and 12 month follow-up assessment time points (phone contacts).

### 8.2.10 Venous Clinical Severity Score (Revised)

---

The VCSS assesses nine common signs/symptoms of venous disease: skin changes and pigmentation, inflammation and induration, and ulcers (including number, size, and duration). A tenth item assesses compression compliance. Each item is scored individually on a 0-3 point scale. The revised VCSS clarifies ambiguities in category descriptions and contains an additional category for compression. Investigator or delegate should complete assessment on source worksheet (SW) and enter data into iDCT.

### 8.2.11 EQ-5D-5L Quality of Life Assessment

---

The EQ-5D-5L is a validated, widely used quality of life assessment. It is a patient reported outcome that provides a simple descriptive profile and single index value for health status. The questionnaire consists of 5 questions pertaining to specific health dimensions, including mobility, self-care, usual activities, pain/discomfort, anxiety/depression, and overall health status rating scale. Subjects should complete questionnaire on SW and data is entered into iDCT.

## 9. ADVERSE EVENTS

---

### 9.1 Definitions

---

**Adverse Event (AE)** any untoward medical occurrence in a patient or clinical investigation subject administered a pharmaceutical product and which does not necessarily have to have a causal relationship with the treatment

An undesirable event can be, but is not limited to, symptoms experienced by a subject or objective findings, such as significant clinical laboratory abnormalities.

**Serious Adverse Event (SAE)** any untoward medical occurrence that at any dose:

- results in death,
- is life-threatening (Note: The term “life-threatening” refers to an event in which the patient was at risk of death at the time of the event; it does not refer to an event which hypothetically might have caused death if it were more severe),
- requires inpatient hospitalization or prolongation of existing hospitalization,
- results in persistent or significant disability/incapacity,
- is a congenital anomaly/birth defect,
- is an important medical event that may not be immediately life-threatening or result in death or hospitalization but may jeopardize the patient or may require intervention to prevent one of the other outcomes listed above

**Adverse Drug Reaction (ADR)** a response to a drug which is noxious and unintended and which occurs at doses normally used in man for prophylaxis, diagnosis, or therapy of disease or for modification of physiological function.

**Unexpected Adverse Event** an AE for which the nature or severity is not consistent with information in the relevant source document(s).

### 9.2 Reporting Adverse Events

---

AEs can occur from the time of initiation of treatment until the subject completes the registry or withdraws. If Investigator or delegate becomes aware of an AE and wishes to report it to the Sponsor/Manufacturer, Investigator or delegate should report the event by sending an Adverse Event Form (Appendix H) via email to [[contact]](mailto:[contact]). Questions about AEs or other safety-related concerns can also be sent via the same email address.

In some cases, Sponsor/Manufacturer may need additional information from investigational site in order to provide a report to the Food and Drug Administration (FDA) to comply with mandatory regulatory reporting. Sponsor will request additional medical information about subject as needed.

If additional safety information becomes available during the course of the registry, Sponsor will amend protocol and ICF as necessary.

---

 ICH E2A Clinical Safety Data Management: Definitions and Standards for Expedited Reporting. 1994.

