## 10.7 Safety Analyses

---

No safety analyses are planned.

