## 12.8 Suspension or Termination of Registry

---

If conditions arise requiring further clarification before the decision can be reached to proceed with or terminate the registry, the registry will be suspended until the situation has been resolved.

Sponsor has the right to terminate this registry at any time. Examples of situations where this might occur include:

- It becomes apparent that enrollment is unsatisfactory with respect to quality and/or quantity or data recording is chronically inaccurate and/or incomplete.
- The incidence and/or severity of adverse events in the registry indicate a potential health hazard caused by the treatment.

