### Section 3. Adverse Events

**Continued on a separate sheet?**

Event No.	Adverse Event Term	Dates of Onset & Resolution (dd/mmm/yyyy)		Outcome of Event 	Causal Relationship 
1		Onset	/ /		
		Resolution	/ /		
2		Onset	/ /		
		Resolution	/ /		
3		Onset	/ /		
		Resolution	/ /		
4		Onset	/ /		
		Resolution	/ /		
5		Onset	/ /		
		Resolution	/ /		

(1) Outcome of Event (enter one code per event): 1 = Fatal 2 = Not Resolved 3 = Resolved 4 = Resolved with Sequelae 5 = Resolving  
(2) Causal Relationship to Varithena (enter one code): 0 = "Not related (no reasonable possibility)" 1 = "Related (reasonable possibility)"

**Section 4. Any relevant medical history/concurrent conditions and clinical progression of the adverse event including labs, diagnostics, etc.?**  Y  N *(If yes, specify below)*

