**Please email the completed form to BTG Vigilance within 48hrs of awareness to**

# Varithena® Venous Leg Ulcer Registry

## Adverse Event Reporting Form V01

### Section 5. Concomitant medications

Only include drugs given within the 30 days prior to AE onset excluding treatment for AE

Drug Name	Brand	Indication for use	Total Daily Dose Prior to this AE (include units)	Freq.	Route of admin.	Date of First Administration of Drug AND Date of Last Administration of Drug Prior to this SAE (dd/mmm/yyyy)	
						First	/ /
						Last	/ /
						First	/ /
						Last	/ /
						First	/ /
						Last	/ /
						First	/ /
						Last	/ /
						First	/ /
						Last	/ /

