3.7 Safety analyses

The number of serious adverse events related to Varithena[®] will be listed.

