3.8 Interim analysis

An interim futility analysis will be performed when approximately 50 – 75 patients have enrolled and completed their 12 week post-treatment follow-up. The futility analysis will look for the following safety concerns:

- Hospitalizations due to target wound
- Serious adverse events related to Varithena[®]

If the analyses show there is a high safety concern, the study will be stopped.

Additionally, the descriptive summaries for the primary endpoints (see section 3.5.1 for further details on the primary endpoints) and the secondary endpoint of EQ-5D-5L (see section 0) and NPRS (see section 0) will be performed. Information on baseline wound characteristics (see section 3.3.2), treatment history (see section 3.4.1), post-treatment ultrasound and occlusion (see section 3.4.1) will be also be summarized.

4 Appendix

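### SAE reporting to the sponsor is discretionary, yet related SAEs are one of two inputs to the interim stop and the only item in the SAP's safety section

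*Protocol*

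**What the plan says.** **Collection.** Protocol 9.1 defines AEs and SAEs in full. Protocol 9.2 then has a form sent only if the investigator or delegate "becomes aware of an AE and wishes to report it to the Sponsor/Manufacturer". There is no separate, binding rule for SAEs. Neither Table 1 nor the visit lists in Protocol 8.1.1 to 8.1.8 contain an AE or SAE item. The Adverse Event Form in Appendix H asks for the completed form "within 48hrs of awareness". Its event table has the event term, dates, outcome and causality. No seriousness field appears in the text available.

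**Use.** Protocol 10.7 says "No safety analyses are planned". SAP 3.7 has one item: "The number of serious adverse events related to Varithena" is to be listed. SAP 3.8 adds a safety look at about 50 to 75 patients who have completed 12 weeks. It has two inputs, target-wound hospitalizations and related SAEs, and a consequence: "If the analyses show there is a high safety concern, the study will be stopped". No numeric threshold is given. Protocol 12.8 also names as a ground for termination: "The incidence and/or severity of adverse events in the registry indicate a potential health hazard caused by the treatment".

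**The other input.** Wound hospitalization has its own row in Protocol Table 1, marked at Day 0, the first follow-up visit, Week 12, both phone calls and Month 12. SAP 3.4.1 summarizes it by visit.

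**The concern.** A rule that stops a study on a count needs that count to be collected. Here one of the two inputs depends first on the investigator learning of the event and then on a wish to report it. Unreported events can only lower the count, and nothing in the plan shows by how much.

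The plan has little to catch what is missed:

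- Under Protocol 8.1.4 the subject does not return to the site between the first follow-up visit and Week 12. Wound care center staff are not delegated (7.1.3) and may not know of the registry. Most of the 12 weeks behind the interim look therefore pass without a scheduled investigator contact.
- Because reporting is optional, not filing a form breaks no rule. In any case, Protocol 12.8.1 asks for deviations to be reported to the sponsor only if they concern consent or eligibility.
- A form that is filed may not show whether the event was serious.

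At stake is the reading of the interim look. A reassuring result on related SAEs could mean few events or few reports. The same holds for the final listing.

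**Working it through.** The documents give no sample-size calculation, error rate or stopping threshold, so there is no design figure to reproduce. The point rests on the text; the arithmetic only shows scale.

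**Step 1: the two stop inputs side by side.**

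| | Target-wound hospitalization | Related SAE |
|---|---|---|
| Asked at a scheduled contact | Yes (Table 1) | No |
| Needs a wish to report | No | Yes (9.2) |
| Seriousness identified | Inpatient stay meets the 9.1 definition | No field seen on Appendix H |
| Would capture thrombosis or hypersensitivity | No | Yes, if reported |

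The scheduled input cannot stand in for the discretionary one.

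**Step 2: what a zero count can exclude.** Let p be the true risk of a related SAE and r the probability that one is reported. The data inform only the product p × r, and nothing collected separates the two.

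- n = 50 or 75: the range in SAP 3.8.
- Reported count = 0: hypothetical.
- r = 100%, 50%, 25%: assumed, since the documents give no figure.

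The exact two-sided 95% upper limit for p × r with 0 of n is 1 − 0.025^(1/n). For p, divide by r.

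- n = 75: 1 − 0.025^(1/75) = 4.8%
- n = 50: 1 − 0.025^(1/50) = 7.1%

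| r | Upper limit on p, n = 50 | Upper limit on p, n = 75 |
|---|---|---|
| 100% | 7.1% | 4.8% |
| 50% | 14.2% | 9.6% |
| 25% | 28.4% | 19.2% |

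**Step 3: the chance of seeing nothing.** P(none reported) = (1 − p × r)^n. With p = 2%, also an assumption:

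| r | n = 50 | n = 75 |
|---|---|---|
| 100% | 0.98^50 = 36% | 0.98^75 = 22% |
| 50% | 0.99^50 = 61% | 0.99^75 = 47% |
| 25% | 0.995^50 = 78% | 0.995^75 = 69% |

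An observed zero is compatible with every row of both tables.

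**The case against.** The strongest defense is that this is a Phase 4 registry of a marketed product used per standard of care, with no safety objective or endpoint. Protocol 4.3 reports no SAEs attributed to treatment in 1333 trial patients. Spontaneous reporting might then be thought enough. That explains Protocol 10.7, but not the later choice in the SAP to attach a study stop to related SAEs. The earlier record may also not carry over. The pivotal trials excluded prior DVT or PE and reduced mobility, and C5 and C6 together made up 5.2% of VANISH-2, whereas every patient here is C6. The documents give no related-SAE rate for such patients.

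A second defense stands in part. If related SAEs are rare, zero is the likely result even with perfect reporting. The exact upper limit for 0/1333 is 1 − 0.025^(1/1333) = 0.28%; at that risk the chance of none among 75 is 81% with full reporting and 90% with half. At 0.9%, the label's figure for proximal symptomatic thrombi, it is 51% and 71%. Better reporting removes a bias; it does not make a look at 50 to 75 patients sensitive to rare events.

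Several stronger readings are tempting but not supported:

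- A reader might infer that related SAEs alone drive the stop, or are the only safety output. Wound hospitalization is a separate input and is tabulated by visit, and SAP 3.3.1 counts deaths in disposition.
- A reader might conclude that the stop gives no protection. The hospitalization input works without AE forms, and Protocol 12.3.1 makes investigators keep the IRB/REB informed of reportable adverse events. That route does not feed the SAP count, but it is a safeguard.
- A reader might take the label's DVT rate for the 1% product (7/149 = 4.7%) as the rate of events at risk of being missed. A DVT is not necessarily a related SAE, and the zero in 1333 argues against using that figure.
- A reader might take the hospitalization question as asked at every contact. Table 1 does not mark it at screening or at the weekly wound care center visits, and the lists in 8.1 do not name it.
- The 48-hour line does not contradict 9.2. It times a completed form and does not require that one be completed.

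One limit remains: the eCRF named in the SAP introduction is not available, so an SAE field there cannot be ruled out. The statement that nobody asks is about the protocol's schedule and visit lists.

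**Conclusion.** The concern holds in this form. Reporting of SAEs to the sponsor is discretionary and no contact scheduled in the protocol asks about them, while related SAEs are one of two inputs to the interim stop and the sole content of SAP 3.7. For drug-related harm the other input is no substitute. The count is biased downward, leaving aside errors in causal attribution, which could go either way.

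The size of the bias is unknown and cannot be estimated from the data to be collected. The illustrated fourfold range at 75 patients, an upper limit from 4.8% to 19.2%, depends on a hypothetical zero count and on assumed reporting fractions from 100% down to 25%, taken as equal for all events. It is not a forecast. The descriptive efficacy analyses are not affected. The point should be addressed because the plan gives this count a decision to make.

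**What to change.** - **Protocol 9.2:** require every SAE, at minimum every related SAE, to be reported on Appendix H within the 48 hours the form already states.
- **Appendix H:** add a seriousness field if the full form lacks one.
- **Table 1 and the visit lists:** add a yes/no question on any SAE since the last contact, beside the hospitalization question, at each post-treatment site visit and phone call.
- **Consistency:** reconcile Protocol 10.7 with SAP 3.7 and 3.8, so that both documents state the same safety analysis and the same source for its counts.

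The cost is a protocol amendment, which under Protocol 12.7 needs approval by investigators, sponsor and IRB/REB, plus a small change to the form and data capture and modest extra reporting by sites. The form and its mailbox exist already. Treatment is not changed.

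If reporting is to stay voluntary, SAP 3.7 and 3.8 should state that the related-SAE count comes from spontaneous reports and that a low count is not evidence of safety.
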